### 7.1.3 Safety Follow-up Period

The follow-up period for this protocol is 7 days +3 days from the last dose of investigational product.

At the end of this period there will be a telephone call initiated by the site staff to query for serious adverse events (SAEs), AEs, and concomitant treatments. All AEs and SAEs that are not resolved at the time of this contact will be followed to closure (see [Section 8.1](#)).

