#### **8.2.4 Serious Adverse Event Collection Timeframe**

All SAEs (regardless of relationship to study) are collected from the time the subject signs the informed consent until the defined follow-up period stated in Section 7.1.3, and must be reported to the Shire Pharmacovigilance Department within 24 hours of the first awareness of the event.

In addition, any SAE(s) considered “related” to the investigational product and discovered by the investigator at any interval after the study has completed must be reported to the Shire Pharmacovigilance Department within 24 hours of the first awareness of the event.

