#### **8.2.5 Serious Adverse Event Onset and Resolution Dates**

The onset date of the SAE is defined as the date the event meets serious criteria. The resolution date is the date the event no longer meets serious criteria, the date the symptoms resolve, or the event is considered chronic. In the case of hospitalizations, the hospital admission and discharge dates are considered the onset and resolution dates, respectively.

In addition, any signs or symptoms experienced by the subject after signing the informed consent form, or leading up to the onset date of the SAE, or following the resolution date of the SAE, must be recorded as an AE, if appropriate.

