## 9.9 Safety Analyses

The Safety Analysis Set based on either the interim analysis dataset or all cumulative data up to study completion, whenever it is appropriate, will be used to report the safety data.

Clinical laboratory tests, vital signs, and ECG findings will be summarized by treatment group and visit using appropriate descriptive statistics. Potentially clinically important findings will also be summarized by treatment group and listed.

Adverse events will be coded using the Medical Dictionary for Regulatory Activities. TEAEs are defined as AEs that start or deteriorate on or after the date of the first dose of investigational product and no later than 3 days following the last dose of investigational product in the double-blind phase.

Treatment-emergent AEs will be summarized. The number and percent of subjects with TEAEs will be calculated for each system organ class, by preferred term, and by treatment. The severity of the TEAEs, the relationship to the investigational product, TEAEs causing study discontinuation, serious AEs and death will also be presented.

The CSHQ will be summarized by treatment group using appropriate descriptive statistics at each visit.

Sleep diary data will be descriptively summarized by treatment group.

A summary and listing of the C-SSRS data will be provided for subjects with a positive response only.

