11.1 Adverse Events

Adverse events will be coded using Version 18.0 or newer of the Medical Dictionary for Regulatory Activities.

An AE (classified by preferred term [PT]) that occurs during the Evaluation Period will be considered a TEAE if it has a start date on or after the first dose of investigational product or if it has a start date before the date of the first dose of investigational product, but increases in severity on or after the date of the first dose of investigational product. If more than 1 AE with the same PT is reported before the date of the first dose of investigational product, then the AE with the greatest severity will be used as the benchmark for comparison to the AEs occurring during the Evaluation Period under the preferred term. An AE that occurs more than 3 days after the date of the last dose of investigational product will not be counted as a TEAE.

An overall summary of number of subjects with TEAEs in each treatment group will be presented by treatment group, including the number and percentage of subjects with any TEAEs, serious TEAEs, TEAEs related to investigational product, TEAEs leading to withdrawal, severe TEAEs, and TEAEs leading to death.

Number and percentage of subjects reporting TEAEs in each treatment group will be tabulated by system organ class (SOC) and PT. TEAEs will be further summarized by maximum severity and relationship to investigational product. If more than 1 AE occurs with the same PT for the same subject, then the subject will be counted only once for that PT using the most severe and most related occurrence for the summarization by severity and by relationship to investigational product.

The incidence of TEAEs, serious TEAEs, and TEAEs leading to withdrawal will be summarized by SOC, PT, and treatment group, sorted in decreasing frequency for subjects on SPD489 then for placebo. The incidence of common ($\geq 2\%$ of subjects in any treatment group) will be summarized by PT and treatment group, sorted in decreasing frequency for subjects on SPD489 and then for placebo.

The number and percentage of subjects reporting TEAEs over the Safety Analysis Set will also be presented by week of AE onset, preferred term and treatment group, where week of AE onset is calculated as (AE occurred date – first dose date + 1) / 7, then rounded up to an integer.

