All information about AEs collected on the electronic case report form will be listed alongside the dose, PT, and SOC. For serious TEAEs, deaths, AEs related to the investigational product, and TEAEs leading to study discontinuation, a separate listing will also be provided.

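### Serious adverse events starting 4 to 7 (up to 10) days after the last dose are collected but enter no by-arm count of serious events

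*SAP*

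**What the plan says.** **Collection.** Protocol Section 8.2.4: "All SAEs (regardless of relationship to study) are collected from the time the subject signs the informed consent until the defined follow-up period". Section 7.1.3 sets the length: "The follow-up period for this protocol is 7 days +3 days from the last dose of investigational product". The telephone call that closes this period is there to "query for serious adverse events (SAEs), AEs, and concomitant treatments".

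**Dating.** Protocol Section 8.2.5: "The onset date of the SAE is defined as the date the event meets serious criteria". For a hospitalization, that is the admission date.

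**Counting.** Protocol Section 9.9 ends the TEAE window "no later than 3 days following the last dose of investigational product in the double-blind phase", and SAP Section 11.1 follows it: "An AE that occurs more than 3 days after the date of the last dose of investigational product will not be counted as a TEAE". Section 11.1 then specifies two by-arm counts of serious events, a row in the overall TEAE summary and an incidence table by system organ class and preferred term. Both are restricted to serious TEAEs.

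**Listing.** SAP Section 11.1 also says: "For serious TEAEs, deaths, AEs related to the investigational product, and TEAEs leading to study discontinuation, a separate listing will also be provided". The serious listing is thus limited to TEAEs, while those for deaths and related events are not. A general listing covers everything: "All information about AEs collected on the electronic case report form will be listed alongside the dose, PT, and SOC". SAP Section 11.8 adds only a listing of the date of the follow-up call.

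**The concern.** The trial follows every child for a week or more after the last dose and asks about SAEs at the end of that time, but the by-arm serious-event tables stop at day 3. SAEs are few in a trial of this size, so a reader comparing arms expects the count to include every SAE collected after first dose. Here the reader would have to search the all-AE listing and rebuild the count by hand.

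Two features of this trial make the gap more than formal.

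- **The dating rule can move an event into it.** If symptoms begin on drug and the child is admitted on day 5 after stopping, the SAE is dated day 5. The earlier symptoms may be tabulated as a TEAE, including as one leading to withdrawal, but the admission is not counted as serious in any arm.
- **Early stopping is expected.** Protocol Section 6.2.3 allows no dose reduction and discontinues children who cannot tolerate the product, and the sample size assumes 20% dropout. The uncounted days are a larger share of observed time for these children than for completers.

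Deaths are affected in the same way. The by-arm row covers only TEAEs leading to death, so a death from an event starting after day 3 would be listed but has no specified by-arm count.

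**Working it through.** The plan states no figure of its own on this point, so the check is a comparison of windows followed by a day count.

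**Inputs**
- TEAE window after last dose: 3 days (Protocol 9.9, SAP 11.1).
- SAE collection after last dose: 7 days, up to 10 (Protocol 7.1.3 and 8.2.4).
- Screening up to 28 days and treatment 42 days (Protocol synopsis).
- 195 children randomized, 20% dropout (Protocol 9.6): 195 × 0.20 = 39 dropouts and 156 completers.

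**Uncounted days per child** = collection window − TEAE window: 7 − 3 = 4 days, or 10 − 3 = 7 days. Of the days after last dose, that is 4/7 = 57% or 7/10 = 70%.

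**Share of observed time** = uncounted days ÷ total days

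| Child | 7-day follow-up | 10-day follow-up |
|---|---|---|
| Completer, from first dose | 4/(42+7) = 8.2% | 7/(42+10) = 13.5% |
| Completer, from consent | 4/(28+42+7) = 5.2% | 7/(28+42+10) = 8.8% |
| Stops at day 21, from first dose | 4/(21+7) = 14.3% | 7/(21+10) = 22.6% |
| Stops at day 7, from first dose | 4/(7+7) = 28.6% | 7/(7+10) = 41.2% |

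These are shares of days, not of events.

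**Expected uncounted SAEs.** The documents give no SAE rate. Assume a risk of 1% to 5% per child, spread evenly from first dose to end of follow-up, and apply the completer share to all 195 children:
- At 1%: 195 × 0.01 × 0.0816 = 0.16, to 195 × 0.01 × 0.1346 = 0.26.
- At 5%: 195 × 0.05 × 0.0816 = 0.80, to 195 × 0.05 × 0.1346 = 1.31.

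**Effect of dropout on that range.** Suppose all 39 dropouts stopped at day 21 and carried the same total risk over their shorter observation:
- Lower end: 156 × 0.01 × 0.0816 + 39 × 0.01 × 0.143 = 0.127 + 0.056 = 0.18.
- Upper end: 156 × 0.05 × 0.1346 + 39 × 0.05 × 0.226 = 1.05 + 0.44 = 1.49.

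Using the completer share for everyone therefore slightly understates the count under this assumption, and the order of magnitude does not change. Rollover to open-label treatment would lower the figures.

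**Whether another output fills the gap**

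| SAE with onset after day 3 | By-arm serious count | Dedicated listing | All-AE listing |
|---|---|---|---|
| Fatal | none | deaths | yes |
| Non-fatal, related | none | related AEs | yes |
| Non-fatal, unrelated | none | none | yes |

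No other SAP section counts these events.

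**The case against.** The strongest reply is that nothing is lost and little is at stake. Every late SAE is in the all-AE listing. Deaths and related events have listings that are not limited to TEAEs, SAEs go to pharmacovigilance within 24 hours, and an external committee reviews safety. The one category without a dedicated output, late non-fatal SAEs judged unrelated, says least about harm from the drug. The expected number is about one at most on an assumed rate, and no trial decision turns on it. All of this stands and limits the weight of the point. It does not supply the missing count, and a count of all SAEs has the merit of not depending on a causality judgement.

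A second reply is that the 3-day window is the protocol's own and has a purpose. Children may enter open-label SPD489 after Visit 6, and ongoing children roll over at once if the interim analysis succeeds, so part of days 4 to 10 may be open-label exposure. That is a good reason to keep the TEAE definition and to end the new count at the first open-label dose. It is not a reason to leave out SAEs in children who do not roll over.

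Third, SAP Section 1 places table and listing specifications in a separate document, which was not available, and Protocol 9.9 speaks of presenting serious AEs without the treatment-emergent qualifier. An all-SAE table may therefore already be planned. However, the protocol sentence sits in a paragraph on TEAEs and can be read either way, and the SAP itself requires no such table.

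**Conclusion.** The point holds. Followed as written, SAP Section 11.1 produces by-arm serious-event counts that omit SAEs the trial has deliberately collected over the last 4 to 7 days of follow-up.

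The likely number is small: about 0.2 to 1.3 events in 195 children, resting on an assumed risk of 1% to 5% per child spread evenly over time. Nothing in the documents suggests that late SAEs would cluster by dose, so no direction of bias between arms is claimed. Nor is any conflict with the protocol claimed, since both documents use the same 3-day TEAE window. The point is worth correcting because, where SAEs are few, a single omitted event can change how the arms compare, and because the correction is cheap. Confidence is high about what the SAP says. What will finally be reported also depends on the table specifications.

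**What to change.** In SAP Section 11.1, add one by-arm table and one listing of all SAEs and deaths on the Safety Analysis Set. The period should run from first dose to the end of the 7 (+3)-day follow-up, or to the first open-label dose for children who roll over. Flag each event as treatment-emergent or not. Keep the 3-day window for TEAEs and the Protocol 8.2.5 onset date for SAEs.

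The cost is a short SAP edit, one table and one listing, all from data already collected. The downside is that a few post-treatment events may enter the SAE count, which the flag separates. If the table specifications already include such an output, one sentence in the SAP requiring it closes the point.

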### **6.2.3 Dosing**

Dosing should begin at approximately 7:00AM ( $\pm 2$  hours) on the morning after the baseline visit (Visit 0). Subjects will be instructed to take 1 capsule daily in the morning throughout the study, at approximately the same time each day. The same parent/LAR should be available daily to dispense the dose of investigational product for the study duration.

SPD489 may be administered in one of the following ways:

- Swallow SPD489 capsule whole, or
- Open capsule, empty and mix the entire contents with yogurt, water, or orange juice.

The contents should be mixed until completely dispersed. The subject must ingest the entire amount of the mixture immediately within 3 minutes. The subject should not take anything less than one capsule per day and a single capsule cannot be split. The empty gelatinous capsule should be discarded into a trash receptacle by the parent/LAR.

Subjects will begin dosing with the lowest strength of SPD489 (5 mg) and will be titrated until the randomly assigned fixed-dose is reached.

Once subjects reach the fixed-dose level, this dose will be maintained until the end of the study.

No dose reductions are permitted during the study. Subjects who are unable to tolerate investigational product will be discontinued.

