### **7.1.2 Double-blind Evaluation Periods**

#### **7.1.2.1 Fixed-dose Titration Period (Visits 1 to 3)**

During the first 3 weeks of treatment, visits will be scheduled every 7 days ( $\pm 3$  days) to assess safety, efficacy, and tolerability and to allow investigators to titrate subjects to their randomly assigned fixed-dose strength.

Subjects who are unable to tolerate investigational product should be discontinued from the study.

Throughout the Fixed-dose titration Period, subjects may attend the clinic for unscheduled visits to address any medical needs that arise between scheduled visits.

See [Table 1](#) for procedures that are completed at Visits 1 to 3. Further clarification for these visits is outlined below:

- At each visit during the Fixed-dose titration Period, subjects must return any empty or unused bottles to permit drug accountability and compliance to be assessed.
- Subjects will be dispensed a 10-count bottle of investigational product to cover them until their next regularly scheduled visit. Subjects will be instructed to take 1 capsule each day. Dosing will begin the morning following each visit.
- Blood pressure and pulse will be collected 3 times (with at least 2 minutes in between each collection) during the visit. The average of each set of 3 measurements will be used to determine continued participation in the study (see [Section 4.4.1](#)).
- Scales should be completed by the same rater with input from the same parent/LAR whenever possible.
- The C-SSRS “Since Last Visit” Version of the Pediatric/Cognitively Impaired Version should be completed during the Fixed-dose titration Period.

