#### **7.1.2.2 Dose-maintenance Period (Visits 4 to 6)**

Following titration to the randomly assigned fixed-dose strength of SPD489/Placebo, subjects will continue daily morning treatment for an additional 3 weeks.

Throughout the Dose-maintenance Period, subjects may attend the clinic for unscheduled visits to address any medical needs that arise between scheduled visits.

[Table 1](#) outlines the procedures to be completed at each visit during the Dose-maintenance Period. Additional clarification on the procedures to be performed during the Dose-maintenance Period is provided below:

- Scales are to be completed by the same rater with input from the same parent/LAR whenever possible
- At each visit during the Dose-maintenance Period, subjects must return any empty or unused bottles to permit drug accountability and compliance to be assessed.
- Subjects will be dispensed a 10-count bottle of investigational product to cover them until their next regularly scheduled visit. Subjects will be instructed to take 1 capsule each day. Dosing will begin the morning following each visit.
- The C-SSRS “Since Last Visit” Version of the Pediatric/Cognitively Impaired Version should be completed during the Dose Maintenance Period.
- After 5 minutes rest, blood pressure and pulse will be collected 3 times (with at least 2 minutes in between each collection) during the visit. The average of each set of 3 measurements will be used to determine continued participation in the study (see [Section 4.4.1](#)).

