### 9.6 Sample Size Calculation and Power Considerations

Approximately 195 subjects will be randomized in a 5:5:5:5:6 ratio to SPD489 5, 10, 20, 30 mg or placebo to achieve 156 completers for the study (30 in each active treatment group and 36 in the placebo group) and 85% power for the primary efficacy analysis at a 2-sided 0.05 significance level. The sample size planned at study initiation is estimated based on the primary comparison between pooled SPD489 10, 20, and 30 mg dose levels (excluding the 5 mg) and placebo on the primary efficacy endpoint, in a group sequential design with 1 interim analysis using the Lan-DeMets alpha spending function with O'Brien-Fleming boundary for the primary efficacy endpoint. Assumptions for the calculation include the true mean difference of 8.4 with the common standard deviation (SD) of 14 for the primary efficacy endpoint, for an effect size of 0.6, and a dropout rate of 20%.

The dose-response relationship that measured as the ADHD-RS-IV Preschool Version Total Score change from baseline will be evaluated separately. Assuming the maximum difference in change from baseline in ADHD-RS-IV Preschool Version Total Score between 0 mg (placebo) and SPD489 (5, 10, 20 or 30 mg) is 13.0 points, and has a standard deviation of 14 for the change, then in order to detect a plausible dose-response curve at 85% power and a significance level of 0.05 (2-sided) using MCP-Mod with equal allocation to the treatment groups, it is necessary to have 18 completers for each arm.

Assuming a 20% dropout rate, a total of 24 subjects for each treatment group are required to be randomized. Therefore, the overall sample size of the study will be sufficient for dose-response analysis.

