4.3 Safety Analysis Set

The Safety Analysis Set will consist of all Randomized Set who have taken at least 1 dose of investigational product.

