8. EXTENT OF EXPOSURE AND TREATMENT COMPLIANCE

8.1 Exposure to Investigational Product

Exposure to double-blind investigational product for the Safety Analysis Set will be summarized by treatment, pooled doses. The following statistics will be calculated for the Fixed-dose Titration Period, the Dose Maintenance Period, and the whole Double-blind Evaluation Period for the investigational product:

- Total days of dosing: sum of the days of dosing for each period. Within each period, it is defined as (date of last dose - date of first dose + 1)
- Average daily dose (mg/day) for SPD489: the total dose/total days of dosing
- Maximum dose for SHP489: the highest dose level received

An appropriate statistical summary will be applied to present for each of the above statistical quantity for each of the study period respectively. In addition, person-time (overall total exposure in days) will be derived. It is calculated as total number of days in which the investigational product was taken for each subject and then sum over all subjects for the whole duration of the study.

Dosing information will be listed.

If a subject is lost to follow-up without returning the leftover investigational product and without providing subsequent safety information, then the subject's dose information will be treated as missing. In particular, for the subjects lost to follow up after the Baseline visit (Visit 0), we will not assume any ingestion of the investigational product unless there is a post-baseline safety assessment. Subjects that do not return the investigational product but return to the site for a following visit will have zero capsule returned entered into the database. In this case, it will be assumed for analysis purposes that all capsules were ingested.

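### Late-week percentages in the TEAE-by-week-of-onset table are understated because the only denominator given, the Safety Analysis Set, keeps children who can no longer contribute an event

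*SAP*

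**What the plan says.** SAP 11.1 plans one adverse-event table that is resolved in time: "The number and percentage of subjects reporting TEAEs over the Safety Analysis Set will also be presented by week of AE onset", split by preferred term and treatment group. Week is counted from the first dose in blocks of 7 days, so week 6 is days 36 to 42. No week-specific denominator is given.

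The Safety Analysis Set (SAP 4.3) is the randomized children "who have taken at least 1 dose of investigational product". Membership does not end when a child stops treatment. The numerator does end: under SAP 11.1, "An AE that occurs more than 3 days after the date of the last dose of investigational product will not be counted" as treatment-emergent.

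On dose, Protocol 6.2.3 says "Subjects will begin dosing with the lowest strength of SPD489 (5 mg) and will be titrated until the randomly assigned fixed-dose is reached". Protocol 7.1.2.1 sets the titration period ("During the first 3 weeks of treatment, visits will be scheduled every 7 days"), and Protocol 7.1.2.2 adds that "subjects will continue daily morning treatment for an additional 3 weeks". Protocol 6.2.3 also rules out dose reductions and has children who cannot tolerate the product discontinued.

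If the study stops at the interim analysis, ongoing children move at once to the extension study (SAP 2.6.2), and safety is reported on the interim dataset plus the overrun (SAP 11).

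SAP 8.1 states: "In addition, person-time (overall total exposure in days) will be derived". This is a whole-study total, and no adverse-event table uses it.

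**The concern.** A percentage by week invites the reader to ask how likely an event was in that week. That requires a denominator of children who could have had one. Here the denominator is fixed on day 1 while the children able to enter the numerator become fewer, so the shown percentage falls below the incidence among children at risk, and falls further each week.

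The later columns matter most. Every active arm starts at 5 mg, so in the arms titrated higher the early columns mix in low-dose exposure, and most of the exposure to the assigned dose lies later. No other table in SAP 11.1 separates early from late onset.

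Elsewhere the SAP avoids the problem. Vital-sign and ECG percentages (SAP 11.3, 11.4) use children with an assessment for that parameter and visit, and qualitative urinalysis (SAP 11.2) uses children with a valid result at baseline and that visit.

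**Working it through.** **Inputs.** 195 randomized, allocation 5:5:5:5:6, 156 completers (Protocol 9.6, SAP 2.5). The same sections give "for an effect size of 0.6, and a dropout rate of 20" per cent, overall, with no figure by arm or week. Treatment lasts 42 days. The TEAE window closes 3 days after the last dose (SAP 11.1).

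**The plan's own figure.** 195 × (1 − 0.20) = 156, as stated. An active arm has 195 × 5/26 = 37.5 children and placebo 195 × 6/26 = 45.

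**Formula.** Shown percentage = incidence among children at risk × (children at risk ÷ Safety Analysis Set).

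**At-risk share.** Assume dropout D is spread evenly over 42 days. Week k starts on day 7(k − 1) + 1. A child is outside the window by then if the last dose was on or before day 7(k − 1) − 3.

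- Start of week, window counted: 1 − D × [7(k − 1) − 3]/42 (for k of 2 or more)
- Start of week, window ignored: 1 − D × (k − 1)/6

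With D = 0.20:

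| Week | Window counted | Window ignored |
|---|---|---|
| 1 | 1.000 | 1.000 |
| 2 | 0.981 | 0.967 |
| 3 | 0.948 | 0.933 |
| 4 | 0.914 | 0.900 |
| 5 | 0.881 | 0.867 |
| 6 | 0.848 | 0.833 |

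For week 6 the first column is 1 − 0.20 × 32/42 = 0.848, an understatement of about 15%. Ignoring the window gives 17% at the start of the week, and 1 − 0.20 × 5.5/6 = 0.817, or 18%, at mid-week.

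**In children.** An active arm has 37.5 × 0.848 = 31.8 at risk at the start of week 6. A 10% incidence is 3.18 children, shown as 3.18/37.5 = 8.5%.

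**Between arms.** If D is equal across arms, the factor cancels and ratios are preserved. If D differs, they are not. As an assumed example, take 30% loss in an active arm and 10% on placebo, even loss, window ignored. The week-6 shares are 1 − 0.30 × 5/6 = 0.750 and 1 − 0.10 × 5/6 = 0.917.

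- An equal true incidence of 10% is shown as 7.5% against 9.2%. With the window counted the shares are 0.771 and 0.924, so 7.7% against 9.2%.
- A true ratio of 1.5 (15% against 10%) is shown as 11.25/9.17 = 1.23.
- With the losses reversed, the same ratio is shown as 13.75/7.50 = 1.83.

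**Interim stop.** The interim falls at 0.60 × 195 = 117 finished children. Enrolment rate is an assumption, taken as 2 to 4 per week. The low end fits Protocol 3.2: about 24 months (some 104 weeks) less 11 weeks leaves 93, and 195/93 = 2.1. Mean time on treatment is 0.8 × 6 + 0.2 × 3 = 5.4 weeks, so about 10.8 to 21.6 children are ongoing. If these are spread evenly over the 6 weeks, about one sixth have reached week 6 (1.8 to 3.6).

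- Full 8-week overrun, in which 16 to 32 more children finish: (133 × 0.848 + 1.8)/143.8 = 0.80 at 2 per week; (149 × 0.848 + 3.6)/170.6 = 0.76 at 4 per week.
- No overrun: (117 × 0.848 + 1.8)/127.8 = 0.79; (117 × 0.848 + 3.6)/138.6 = 0.74.

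The week-6 understatement then rises from about 15% to roughly 20–26%.

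**The case against.** **The phrase may name a population rather than a denominator.** In SAP 11.2 to 11.4 the denominators are spelled out, the sentence in SAP 11.1 has no such wording, and table specifications sit in a separate document (SAP 1). This reading is possible. But the Safety Analysis Set is the only denominator offered for this table, and on the other reading the denominator is undefined and the same sentence is still needed.

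**A fixed denominator is a legitimate crude measure.** It matches the overall TEAE table, whereas an at-risk denominator describes children who stayed, a selection made after randomization that may differ by arm. This stands as a limit on interpretation. Printing the weekly number at risk and keeping the counts lets a reader see both.

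**Tolerability at the assigned dose does not rest on this table alone.** Exposure is summarized by period (SAP 8.1) and discontinuations by arm and reason (SAP 5). TEAEs leading to withdrawal are tabulated and events are listed with dose (SAP 11.1). Vital signs and ECG are given by visit (SAP 11.3, 11.4). This stands, and it lowers the stakes.

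**Two stronger readings are tempting but unsupported.** A reader might infer that the table flatters the higher doses against placebo. The rule on intolerance makes greater loss there plausible, but the documents give no dropout by arm, and lack of efficacy is also a listed reason for discontinuation (Protocol 4.4.2), which could remove placebo children. The direction between arms is open. A reader might also infer that the later weeks are the only ones on 20 or 30 mg. The weekly titration steps are not in the available text; with one step per week (an assumption), 20 mg would begin in week 3.

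**Conclusion.** The point holds as a modest defect in one descriptive table. With any dropout, the later-week percentages in the week-of-onset table understate incidence among children who could still have an event. At the planned 20% dropout, spread evenly, the week-6 shortfall is about 15% relative, or 1.5 percentage points on a 10% incidence; it is 17–18% if the 3-day window is ignored. After an interim efficacy stop it is larger, by an amount that depends on enrolment and overrun.

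Distortion between arms is conditional on unequal loss, and the 30% and 10% figures are illustrations only. Even timing of dropout is also an assumption. Nothing here affects the overall TEAE tables, any hypothesis test or the type I error.

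**What to change.** In SAP 11.1, define the denominator for week k as the children in that arm who, at the start of week k, are still within the TEAE window (no more than 3 days past the last dose) and not past the data cut or rollover to the extension study. Print that number in each column and keep the event counts. Every counted event then comes from a child in the denominator.

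The cost is one SAP sentence and one changed denominator, derived from dose, data-cut and rollover dates, with no new data. The downside is that late-week percentages become slightly less favourable and describe only children still on treatment, which a table footnote should say.
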